#### 13.7 Cancel

A patient is deemed a *cancel* if he/she is removed from the study for any reason before any study treatment is given. On-study material and the End of Active Treatment/Cancel Notification Form must be submitted. No further data submission is necessary.

## **14.0 Body Fluid Biospecimens**

None.

## **15.0 Drug Information**

### **15.1 Daratumumab (Darzalex Faspro™, Darzalex™, JNJ-54767414)**

**15.11 Background:** Daratumumab is an antineoplastic agent that is an antibody against the CD-38 antigen expression on cells including multiple myeloma.

SQ formulation: Daratumumab and hyaluronidase-fihj injection is a sterile, preservative-free, colorless to yellow, and clear to opalescent solution supplied in a single-dose vial for subcutaneous administration. Each 15 mL single-dose vial contains 1800 mg daratumumab and 30,000 units hyaluronidase, L-histidine, L-histidine hydrochloride monohydrate, L-methionine, polysorbate 20, sorbitol, and Water for Injection, USP.

IV formulation: Daratumumab drug product is a colorless to yellow liquid concentrate. It is presented at a target concentration of 20 mg/mL in a 6R or 25R vial with a nominal fill volume of 5 mL or 20 mL, respectively. It is administered by the intravenous (IV) route after dilution in a sterile, pyrogen-free physiological saline solution (0.9% NaCl) provided by the investigation site. The diluent is a commercially available product approved by the competent authority of the relevant country.

Daratumumab drug product is formulated as a concentrate of 20.0 mg/mL  $\pm$  2.0 mg/mL in an isotonic buffer consisting of sodium acetate, sodium chloride, mannitol and polysorbate 20 at pH 5.5.

### **15.12 Storage and handling:**

The daratumumab vials should be stored in the original carton in a refrigerator at 2°C to 8°C and must not be utilized after the expiry date printed on the label. The product must be protected from light and must not be frozen. Since daratumumab does not contain preservatives, any unused portion remaining in the vial must be discarded.

IV: Daratumumab will be diluted in a sterile, pyrogen-free physiological saline solution (0.9% NaCl) prior to IV administration.

SQ: Daratumumab and hyaluronidase-fihj SC injection is directly drawn from the vial into a syringe and is compatible with polypropylene or polyethylene syringe material; polypropylene, polyethylene, or polyvinyl chloride (PVC) subcutaneous infusion sets; and stainless steel transfer and injection needles. After the solution is withdrawn into the syringe, replace the transfer needle with a syringe cap. To avoid needle clogging, attach the hypodermic injection needle or subcutaneous infusion set to the syringe immediately prior to injection.

#### 15.14 Pharmacokinetic information:

Pharmacokinetic (PK) data are available from GEN501, MMY2002 and MMY1002 monotherapy studies. Doses across these studies ranged from 0.005 to 24 mg/kg. The PK profile was consistent with target-mediated disposition with rapid target-related clearance at low doses and slower clearance at higher doses. Preliminary PK data from Study GEN503 show that following both the first dose and multiple repeated doses, the PK profile of daratumumab in combination with lenalidomide and dexamethasone is similar to what was observed in Study GEN501 following the same dose and schedule. The data suggest that lenalidomide and dexamethasone do not affect the PK profile of daratumumab.

Overall, biomarker assessments evaluated to date provided evidence of NK cell reduction with daratumumab single agent or combination treatment. Increases in T-cell counts and clonality were observed providing preliminary evidence of the immunomodulatory effects of daratumumab that needs further investigation. No significant changes in other immune subsets were observed with daratumumab treatment. A large overlap in baseline CD38 expression was observed between responders and non-responders along with its reduction with daratumumab treatment irrespective of response.

Following the administration of the recommended dose of 1,800 mg daratumumab and 30,000 units hyaluronidase subcutaneously once weekly for 8 weeks, the mean  $\pm$  standard deviation (SD) maximum trough concentrations ( $C_{\text{trough}}$  following the 8th dose) were  $593 \pm 306 \mu\text{g/mL}$  compared to  $522 \pm 226 \mu\text{g/mL}$  for daratumumab 16 mg/kg administered intravenously, with a geometric mean ratio of 108% (90% CI: 96, 122). The estimated median daratumumab area under the concentration-time curves (AUC0-7 days) and daratumumab peak concentration ( $C_{\text{max}}$ ) following the 8th dose were comparable between subcutaneous and intravenous daratumumab ( $4017 \mu\text{g/mL}\cdot\text{day}$  vs.  $4,019 \mu\text{g/mL}\cdot\text{day}$  for AUC0-7 days and  $592 \mu\text{g/mL}$  vs.  $688 \mu\text{g/mL}$  for  $C_{\text{max}}$ ). The absolute bioavailability of daratumumab-hyaluronidase is 69%, with peak concentrations occurring around 3 days ( $T_{\text{max}}$ ). The estimated mean (coefficient of variation, CV) volume of distribution for the central compartment is 5.2 L (37%) and peripheral compartment was 3.8 L with the daratumumab-hyaluronidase formulation. Daratumumab is cleared by parallel linear and nonlinear saturable target mediated clearances. The estimated mean (CV%) linear clearance of daratumumab is 119 mL/day. The estimated mean (CV%) elimination half-life associated with linear clearance is 20 days (22%).

**Body Weight (BW):** After administration of 1,800 mg daratumumab and 30,000 units hyaluronidase subcutaneously once weekly for 8 weeks, the mean maximum  $C_{\text{trough}}$  was 12% lower in the higher body weight group ( $>85 \text{ kg}$ ) while the mean maximum  $C_{\text{trough}}$  was 81% higher in the lower BW group ( $\leq 50 \text{ kg}$ ) compared to the corresponding BW groups in the intravenous daratumumab arm.

#### 15.15 Known potential toxicities:

- **Very Common ( $\geq 10\%$ ):**
  - Blood and lymphatic system disorders: neutropenia, thrombocytopenia, anemia, lymphopenia
  - Gastrointestinal disorders: nausea, vomiting, diarrhea, constipation
  - Infections and infestations: upper respiratory tract infection, bronchitis, pneumonia, nasopharyngitis
  - Injury, poisoning and procedural complications: infusion related reaction
  - Metabolism and nutrition disorders: hypokalemia, hyperglycemia, decreased appetite
  - Musculoskeletal and connective tissue disorder: muscle spasms, back pain, arthralgia, pain in extremity, bone pain, musculoskeletal chest pain
  - Nervous system disorders: dizziness, headache, tremor
  - Psychiatric disorders: Insomnia, anxiety

- Respiratory, thoracic and mediastinal disorders: cough, dyspnea, nasal congestion
- Vascular disorders: hypertension
- General disorders and administration site conditions: fatigue, pyrexia, chills, peripheral edema, asthenia, non-cardiac chest pain, pain
- **Common (1 to <10%):**
  - General disorders and administration site conditions: injection site reaction, peripheral edema
  - Infections and infestations: respiratory tract infection, influenza, lower respiratory tract infection, sepsis, sinusitis, rhinitis, pharyngitis, viral respiratory tract infection, nasopharyngitis, respiratory syncytial virus infections, laryngitis, tonsillitis, lung infection, herpes zoster
  - Blood and lymphatic disorders: febrile neutropenia
  - Cardiac disorders: atrial fibrillation
  - Respiratory, thoracic, and mediastinal disorders: pulmonary edema, hypoxia, laryngeal edema, pneumonitis, bronchospasm
- **Uncommon and rare known potential toxicities, <1%:**
  - Infections and infestations: metapneumovirus infection, tracheitis, acute sinusitis, bronchiolitis, epiglottitis, oropharyngeal candidiasis, rhinovirus infection, tracheobronchitis, upper respiratory tract bacterial infection, infectious bronchitis, infectious laryngitis, infectious pharyngitis, viral rhinitis, respiratory syncytial virus, infectious pneumonia
  - Blood and Lymphatic Disorders: neutropenic sepsis, neutropenic infection

Please refer to the prescribing information or package insert for a more complete comprehensive list of treatment-related adverse events

15.16 **Drug procurement:** Drug will be procured from the commercial supply of daratumumab.

15.17 **Special populations:**

- **Geriatric use:** Of the 237 subjects treated with daratumumab monotherapy in clinical studies, 44% were 65 years and over. No overall differences in safety or effectiveness were observed between these subjects and younger subjects, and other reported clinical experience has not identified differences in responses between the elderly and younger subjects, but greater sensitivity of some older individuals cannot be ruled out. Based on population PK analysis, age (range: 31 to 84 years) had no clinically important effect on the PK of daratumumab, and the exposure of daratumumab was similar between younger (age <65 years, n=127) and older patients (age ≥65 years, n=96). No dose adjustments are considered necessary.
- **Renal impairment:** No formal studies of daratumumab in subjects with renal impairment have been conducted. Changes in renal function are unlikely to have an effect on the elimination of daratumumab since daratumumab is not excreted via renal pathways. Based on a population pharmacokinetic (PK) analysis no dosage adjustment is necessary for subjects with renal impairment. Daratumumab has not been studied in

subjects with severe renal impairment (creatinine clearance <20 mL/min) or on hemodialysis.

- **Hepatic Impairment:** No formal studies of daratumumab in subjects with hepatic impairment have been conducted. Changes in hepatic function are unlikely to have any effect on the elimination of daratumumab since IgG1 molecules such as daratumumab are not metabolized through hepatic pathways. Based on a population PK analysis, no dosage adjustments are necessary for subjects with mild hepatic impairment (Total Bilirubin [TB] 1.0× to 1.5× upper limit of normal [ULN] or aspartate aminotransferase [AST] >ULN). Daratumumab has not been studied in subjects with moderate to severe hepatic impairment (TB >1.5× ULN and any AST).

#### 15.18 Nursing Guidelines

- Daratumumab can cause severe infusion reactions, usually during the first infusion. Patients who have experienced a reaction may experience further reactions with subsequent infusions. Most reactions occur during or within 4 hours of infusion, however, may occur up to 48 hours after an infusion. Warn patient of this possibility. Monitor patient throughout infusion for bronchospasm, hypoxia, SOB, and hypertension. Patients may also experience symptoms of anaphylaxis. Administer emergency medication as ordered.
- Patients may experience infections, including URI and pneumonia. Patients who have an ongoing infection should not receive agent.
- Patients may experience gastrointestinal side effects including diarrhea and nausea. Treat symptomatically and monitor for effectiveness.
- Warn patients about the possibility of peripheral neuropathy, dizziness, and insomnia.
- Fatigue is common. Instruct patient in energy conserving lifestyle.
- Rarely patients may experience cardiac issues including, atrial-fibrillation, peripheral edema, and hypertension. Instruct patient to report any chest pain, heart palpitations, and swelling to the study team.
- Monitor CBC w/diff as cytopenias (thrombocytopenia, neutropenia, anemia, and lymphopenia) have been seen. Instruct patient to report any unusual, bruising, bleeding, and/or infections/fever to the study team.

#### 15.2 Lenalidomide for Oral Administration (Revlimid®)

##### 15.21 Background:

Lenalidomide has antineoplastic, immunomodulatory and antiangiogenic characteristics via multiple mechanisms. Lenalidomide selectively inhibits secretion of proinflammatory cytokines (potent inhibitor of tumor necrosis factor-alpha secretion); enhances cell-mediated immunity by stimulating proliferation of anti-CD3 stimulated T cells (resulting in increased IL-2 and interferon gamma secretion); inhibits trophic signals to angiogenic factors in cells. Lenalidomide inhibits the growth of myeloma cells by inducing cell cycle arrest and cell death.

##### 15.22 Formulation and Dispensing:

Commercially available for oral administration as: Capsules: 5 mg, 10 mg, 15 mg and 25 mg

Lenalidomide is approved for marketing only under a FDA approved, restricted distribution program called Revlimid REMS. Physicians, pharmacies, and patients must be registered; a maximum 28-day supply may be dispensed; a new

prescription is required each time it is filled; pregnancy testing is required for females of childbearing potential.

15.23 **Preparation, storage, and stability:** Store oral capsules at controlled room temperature between 15°C and 30°C (59 °F and 86 °F). Refer to labeling on the bottle for expiration date of the commercial tablets.

15.24 **Administration:** Refer to the treatment section for specific administration instructions. Administer with water. Swallow capsule whole; do not break, open, or chew.

15.25 **Pharmacokinetic information:**  
**Absorption:** Rapid  
**Metabolism:** Approximately two-thirds of Lenalidomide is eliminated unchanged through urinary excretion.  
**Protein binding:** ~30%  
**Time to peak, plasma:** Healthy volunteers: 0.6-1.5 hours; Myeloma patients: 0.5-4 hours  
**Half-life elimination:** ~3 hours  
**Excretion:** Urine (~67% as unchanged drug)

15.26 **Potential Drug Interactions:**  
**Increased Effect/Toxicity:** Abatacept and Anakinra may increase the risk of serious infection when used in combination with Lenalidomide. Lenalidomide may increase the risk of infections associated with vaccines (live organism).  
**Decreased Effect:** Lenalidomide may decrease the effect of vaccines (dead organisms).  
**Herb/Nutraceutical Interactions:** Avoid echinacea (has immunostimulant properties; consider therapy modifications).

15.27 **Known potential adverse events:** Consult the package insert for the most current and complete information.

**Boxed Warnings:**

1. Potential for human birth defects
2. Hematologic toxicity (neutropenia and thrombocytopenia)
3. Deep Venous Thrombosis and Pulmonary Embolism

**Common known potential toxicities, >10%:**

Cardiovascular: Peripheral edema

Central nervous system: Fatigue, pyrexia, dizziness, headache

Dermatologic: Pruritus, rash, dry skin

Endocrine & metabolic: Hyperglycemia, hypokalemia

Gastrointestinal: Diarrhea, constipation, nausea, weight loss, dyspepsia, anorexia, taste perversion, abdominal pain

Genitourinary: Urinary tract infection

Hematologic: Thrombocytopenia, neutropenia, anemia, myelosuppression is dose-dependent and reversible with treatment interruption and/or dose reduction

Neuromuscular & skeletal: Muscle cramp, arthralgia, back pain, tremor, weakness, paresthesia, limb pain

Ocular: Blurred vision

Respiratory: Nasopharyngitis, cough, dyspnea, pharyngitis, epistaxis, upper respiratory infection, pneumonia

**Less common known potential toxicities, 1% - 10%:**

Cardiovascular: Edema, deep vein thrombosis, hypertension, chest pain, palpitation, atrial fibrillation, syncope

Central nervous system: Insomnia, hypoesthesia, pain, depression

Dermatologic: Brusing, cellulitis, erythema

Endocrine & metabolic: Hypothyroidism, hypomagnesemia, hypocalcemia

Gastrointestinal: Vomiting, xerostomia, loose stools

Genitourinary: Dysuria

Hematologic: Leukopenia, febrile neutropenia, Lymphopenia

Hepatic: ALT increased

Neuromuscular & skeletal: Myalgia, rigors, neuropathy

Respiratory: Sinusitis, rhinitis, bronchitis, pulmonary embolism

Miscellaneous: Night sweats, diaphoresis

**Rare known potential toxicities, <1% (Limited to important or life-threatening):**

Angioedema, Stevens-Johnson Syndrome and Toxic Epidermal Necrolysis

Tumor Lysis Syndrome

15.28 **Drug procurement:** As a requirement of the REMS program, access to Lenalidomide is restricted. Lenalidomide is approved for marketing only under a FDA approved, restricted distribution program called REVCLIMID REMS ([www.REVCLIMIDREMS.com](http://www.REVCLIMIDREMS.com)) formerly known as the RevAssist program. Physicians, pharmacies, and patients must be registered; a maximum 28-day supply may be dispensed; a new prescription is required each time it is filled; pregnancy testing is required for females of childbearing potential.

15.29 **Nursing Guidelines:**

- Myelosuppression is dose-dependent and reversible with treatment interruption and/or dose reduction. Monitor CBC w/diff regularly. Instruct patient to report any unusual bruising or bleeding (thrombocytopenia); signs and symptoms of infection (neutropenia); and energy conserving lifestyle (anemia).
- Lenalidomide can have thrombotic adverse events (i.e DVT and PE). Instruct patient to report any limb swelling or pain, and to seek medical attention for shortness of breath or chest pain.
- Because of the potential for birth defects patients should be instructed in effective methods of birth control. Female patients should use 2 forms of birth control during treatment and for 4 weeks after discontinuing therapy. Males must be instructed to use a latex condom during any sexual contact with a woman of child bearing potential (even if they have had a vasectomy), because it is unknown if lenalidomide is present in semen.
- Patients may experience pruritus, rash and dry skin. Because of the rare risk of Steven's Johnson Syndrome, patients should immediately report any rash to their provider.
- Drug may cause hyperglycemia. Patients with diabetes or impaired fasting glucose may need to have their glucose levels monitored more closely.

- Gastrointestinal side effects (diarrhea, constipation, nausea, dyspepsia, anorexia, etc) are commonly seen. Manage patient symptomatically and monitor for effectiveness.
- Patients may experience myalgias, arthralgias, and other generalized pain. Administer analgesics as ordered and monitor for their effectiveness.
- Upper respiratory symptoms (nasopharyngitis, cough, epistaxis, etc.) can be seen. Manage symptomatically and monitor for effectiveness.

## 16.0 Statistical Considerations and Methodology

### 16.1 Overview

This is a phase II study of Daratumumab for transplant eligible multiple myeloma patients. This study is designed to assess the rate of minimal residual disease (MRD) negativity using a one stage phase II study design with an interim analysis in patients with transplant eligible multiple myeloma.

- 16.11 Primary Endpoint: The primary endpoint of this study is the rate of MRD negative response after ASCT. MRD negative response after ASCT is defined as achievement of MRD negative status in the bone marrow by flow cytometry (MPF) at the day 100 post ASCT visit. All patients meeting the eligibility criteria, who have signed a consent form and have begun treatment will be evaluable for response, unless they are determined to be a major violation.
- 16.12 Sample Size: The one stage study design with an interim analysis to be used is fully described below. A minimum of 20 and a maximum of 45 evaluable patients will be accrued total onto this phase II study unless undue toxicity is encountered. We anticipate accruing an additional 5 patients to account for ineligibility, cancellation, major treatment violation, or other reasons for a total of 50 patients overall.
- 16.13 Accrual Rate and Study Duration: The anticipated accrual rate is 2 evaluable multiple myeloma patients per month. Therefore, the accrual period for this phase II study is expected to be about 2 years. The maximum total study duration is expected to be approximately 5 years, or until the last patient accrued has been observed at least for 3 years after registration.

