16.314 NOTE: We will not suspend accrual at the interim analysis to allow the first 20 patients to become evaluable, unless undue toxicity is observed. Given the limited overall sample size and the inclusion of an adverse events stopping rule, we feel it is ethical to not halt accrual for the interim analysis. However, if accrual is extremely rapid, we may temporarily suspend accrual in order to obtain safety data on these patients before re-opening accrual to further patients.

16.32 Power and Significance Level: Assuming that the number of successes is binomially distributed, the significance level is .09, i.e. there is a 9% chance of finding the drug to be effective when it truly is not. The probability of declaring that this regimen warrants further study (i.e. statistical power) and the probability of stopping at the interim analysis under various success proportions can be tabulated as a function of the true success proportion as shown in the following table.

If the true success proportion is...	0.45	0.50	0.55	0.60	0.65
Then the probability of declaring that the regimen warrants further study is...	0.09	0.25	0.49	0.74	0.90
And the probability of stopping at the interim analysis is...	0.59	0.41	0.25	0.13	0.05

16.33 Other considerations: Adverse events, quality/duration of response, and patterns of treatment failure observed in this study, as well as scientific discoveries or changes in standard care will be taken into account in any decision to terminate the study.

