#### 16.4 Analysis Plan

The analysis for this trial will commence at planned time points (see 16.2) and at the time the patients have become evaluable for the primary endpoint. The Statistician and Study Chair will make the decision, in accord with CCS Standard Operating Procedures, availability of data for secondary endpoints (e.g., laboratory correlates), and the level of data maturity. It is anticipated that the earliest date in which the results will be made available via manuscript, abstract, or presentation format is all patients have been

followed at least through the day 100 post ASCT visit (approximately 8 months) or have discontinued study treatment prior to ASCT.

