#### 16.41 Primary Outcome Analysis:

16.411 Definition: The primary endpoint of this trial is the rate of MRD negative response after ASCT. MRD negative response after ASCT is defined as achievement of MRD negative status in the bone marrow by flow cytometry (MPF) at the day 100 post ASCT visit. All patients meeting the eligibility criteria who have signed a consent form and have begun treatment will be evaluable for response, unless they are determined to be a major violation.

16.412 Estimation: The proportion of successes will be estimated by the number of successes divided by the total number of evaluable patients. Ninety-five percent confidence intervals for the true success proportion will be calculated according to the approach of Duffy and Santner.

16.413 Over Accrual: If more than the target number of patients are accrued, the additional patients will not be used to evaluate the stopping rule or used in any decision making processes; however, they will be included in final point estimates and confidence intervals

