#### 16.52 Adverse Event Stopping Rules:

The stopping rules specified below are based on the knowledge available at study development. We note that the Adverse Event Stopping Rule may be adjusted in the event of either (1) the study re-opening to accrual or (2) at any time during the conduct of the trial and in consideration of newly acquired information regarding the adverse event profile of the treatment(s) under investigation. The study team may choose to suspend accrual because of unexpected adverse event profiles that have not crossed the specified rule below.

Accrual will be temporarily suspended to this study if at any time we observe events considered at least possibly related to study treatment (i.e. an adverse event with attribute specified as “possible,” “probable,” or “definite”) that satisfy one of the following:

- If 5 or more patients in the first 15 treated patients experience a grade 4 or higher non-hematologic adverse event at least possibly related to treatment.
- If after the first 15 patients have been treated, 30% of all patients experience a grade 4 or higher non-hematologic adverse event at least possibly related to treatment.

We note that we will review grade 4 and 5 adverse events deemed “unrelated” or “unlikely to be related”, to verify their attribution and to monitor the emergence of a previously unrecognized treatment-related adverse event.

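### The minimum of 20 evaluable patients in 16.12 is a formal lower bound: with accrual not paused, about 36 of 45 are projected to be enrolled when the futility rule can be applied

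*Combined protocol and SAP*

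**What the plan says.** Section 16.12 sets the size: "A minimum of 20 and a maximum of 45 evaluable patients will be accrued total onto this phase II study unless undue toxicity is encountered". Section 16.311 ends the study if 9 or fewer of the first 20 evaluable patients succeed and otherwise continues accrual; 16.312 then enters 25 more and requires at least 25 successes in 45.

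Success is MRD negativity by bone marrow flow cytometry at the Day 100 post-transplant visit. Under 16.11, "All patients meeting the eligibility criteria, who have signed a consent form and have begun treatment will be evaluable for response", major violations excepted, so a patient lost before Day 100 stays in the denominator. Section 16.412 confirms this: "The proportion of successes will be estimated by the number of successes divided by the total number of evaluable patients".

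On timing, 16.13 says "The anticipated accrual rate is 2 evaluable multiple myeloma patients per month", and 16.4 refers to patients being "followed at least through the day 100 post ASCT visit (approximately 8 months").

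Section 16.314 says "We will not suspend accrual at the interim analysis to allow the first 20 patients to become evaluable", undue toxicity excepted. Its reasons begin "Given the limited overall sample size and the inclusion of an adverse events stopping rule". It also allows a discretionary pause for safety data if accrual is extremely rapid. Section 16.52 adds the safety rule: "Accrual will be temporarily suspended to this study if at any time we observe events considered at least possibly related to study treatment", subject to the thresholds listed there.

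**The concern.** The only enrolment figure the plan ties to the interim look is 20. Read with 16.311 and 16.312, it suggests a trial that enrols 20, looks, and enrols 25 more only if the look is passed. Section 16.314 describes a different conduct, and no section puts the rate, the lag and the no-pause rule together to say how many patients will be in the trial when the rule is applied.

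What is at stake is exposure, not inference. If the regimen is no better than the null, a futility stop is the likelier outcome. A DSMB or IRB weighing the judgement in 16.314 that continuing is ethical would want the number enrolled by then, and the figure in 16.12 does not supply it.

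**Working it through.** **Inputs.** Rate 2 evaluable patients per month (16.13). Lag to Day 100 about 8 months (16.4, 16.6). Interim rule 9 or fewer of 20, final rule 25 or more of 45, null 0.45, alternative 0.65 (16.31). For the range of lags: up to 28 days from registration to treatment (6.15), 28-day cycles with the last Consolidation 1 cycle up to 84 days (7.11), Day 100 visit 90 to 110 days after transplant (7.12), daratumumab omission of at most 28 days in Consolidation 1 (8.1, 8.3).

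**Step 1: reproduce the plan's figures.** With X1 the successes in the first 20, P(stop) = P(X1 ≤ 9 | 20, p). P(promising) = sum over x1 = 10 to 20 of P(X1 = x1) × P(at least 25 − x1 successes in 25).

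| True p | Stop at interim | Declared promising |
|---|---|---|
| 0.45 | 0.591 | 0.090 |
| 0.50 | 0.412 | 0.249 |
| 0.55 | 0.249 | 0.491 |
| 0.60 | 0.128 | 0.735 |
| 0.65 | 0.053 | 0.900 |

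These match the table in 16.32 (alpha 0.0903, power 0.9001). The formulas use only the outcomes of the first 20 and first 45 evaluable patients, so pausing or not pausing makes no difference. Accrual of 45/2 = 22.5 months agrees with the plan's figure of about 2 years.

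**Step 2: enrolment when the first 20 can be judged.** Patient 20 enters at 20/2 = 10 months and reads out at 10 + 8 = 18 months. Enrolled by then: 18 × 2 = 36. Still to enrol: 45 − 36 = 9.

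**Step 3: vary lag and rate.** Enrolled = 20 + rate × lag, with 30.44 days per month.

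| Path to Day 100 | Days | At 2/month | At 1/month |
|---|---|---|---|
| Two cycles, no gap, Day 90: 28+28+90 | 146 | 29.6 | 24.8 |
| Two cycles, full gap, Day 110: 28+84+110 | 222 | 34.6 | 27.3 |
| Same, plus 28-day start window | 250 | 36.4 | 28.2 |
| Four cycles, full gap, Day 110: 84+84+110 | 278 | 38.3 | 29.1 |
| Same, plus start window | 306 | 40.1 | 30.1 |
| Same, plus a 28-day hold | 334 | 41.9 | 31.0 |

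The stated 8 months gives 36 and 28. At 2 per month a futility stop spares between 45 − 29.6 = 15.4 and 45 − 41.9 = 3.1 patients. If arrivals are Poisson, the 16 expected during an 8-month lag range from 10 to 23 (5th to 95th percentile), that is 30 to 43 enrolled. To have even 22 enrolled at an 8-month lag needs 2/8 = 0.25 per month, at which 45 patients take 180 months.

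**Step 4: expected accrual at p = 0.45.** Without a pause: 0.591 × 36 + 0.409 × 45 = 39.7. Had accrual paused at 20: 0.591 × 20 + 0.409 × 45 = 30.2.

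**Step 5: applying the existing rule when its result is certain.** Nine or fewer successes in 20 is the same event as 11 or more failures. P(11th failure is patient j) = C(j−1, 10) × 0.55^11 × 0.45^(j−11) for j = 11 to 20. This sums to 0.591, with mean j = 17.3 given a stop. Mean enrolled at a futility stop: 17.3 + 2 × 8 = 33.3, against 36. Expected accrual: 0.591 × 33.3 + 0.409 × 45 = 38.1, against 39.7.

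This assumes every failure is known only at the Day 100 lag. If, as an assumption, 10%, 20% or 30% of patients leave before transplant and are known as failures at 3 months (success rate still 0.45), simulation gives mean enrolment at a futility stop of 35.9, 35.7 and 35.5 under the rule as written, and 32.5, 31.3 and 29.7 with the earlier trigger.

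**The case against.** The strongest reply is that nothing stated is false. A minimum of 20 is a lower bound, and an expected 36 does not contradict it. The plan prints the rate and the lag, calls the design one-stage with an interim analysis, and discloses and defends the choice not to pause directly after the decision rules. Section 16.311 speaks of continuing accrual, not resuming it. All of this stands. What remains is that the plan discloses the policy but not its consequence, and leaves 20 as the only number attached to the look.

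A reader might infer more: that the design's error rates or stopping probabilities are wrong, that an expected sample size is misstated, or that the absence of a pause is hidden. The documents support none of these. The operating characteristics reproduce, no expected sample size is given, and 16.314 is explicit.

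Two further replies are fair. The plan's review at least twice a year (16.51) and its allowance for patterns of treatment failure in a termination decision (16.33) already permit earlier action, so the earlier trigger is an improvement and not the repair of an error. The point may also be overtaken: activation on April 9, 2018 plus 18 months is about October 2019, well before Amendment 8 of February 26, 2021. The documents do not give actual accrual.

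**Conclusion.** The point holds as a minor one about what the plan communicates. At the planned rate and lag about 36 of 45 evaluable patients are projected to be enrolled when the first 20 can be judged, and no timing path at 2 per month brings that below about 30. A futility stop then saves about 9 patients, not the 25 that a pause at 20 would save.

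The projection rests on steady accrual at 2 evaluable patients per month, on the first 20 being taken in order of entry, and on neither pause in 16.314 being used. An early toxicity stop or suspension, or far slower accrual, could leave enrolment near 20. No inference, decision threshold or maximum sample size changes.

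**What to change.** 1. In 16.12, state that 20 is the number of evaluable patients analysed at the interim and 45 the maximum evaluable, and that either may be cut short by undue toxicity. Add that, because accrual is not paused, about 36 evaluable patients are projected to be enrolled at the interim at 2 per month, a projection that varies with rate and time to Day 100. If the interim has already taken place, give the actual number instead.
2. In 16.311 and 16.312, say that accrual proceeds toward 45 while the first 20 mature, and that evaluable patients already enrolled count toward the additional 25.
3. If the interim has not yet been judged, apply the rule in 16.311, with the consequence it already states, as soon as the 11th of the first 20 evaluable patients can no longer be a success under 16.11. Alpha and power do not change.

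Items 1 and 2 cost a few sentences and a slightly less favourable stated figure. Item 3 costs running tracking of failures among the first 20 and gains about 2.7 patients per futility stop (36 − 33.3), or 1.6 in expected accrual at the null (39.7 − 38.1). It can be declined without affecting the other two. None of the three adds patients or a pause.
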